#### **3.1.2 Dose Expansion (Part 2)**

The purpose of the cohort expansion will be to assess preliminary antitumor efficacy, expanded safety experience, and PD effects of BMS-986148. Additional subjects will be treated after the completion of Part 1A and/ or Part 1B, at the MTD, or at an alternative dose below MTD as agreed upon by the BMS Medical Monitor and investigators. Part 2 can begin before the completion of Part 1B as the Q3W dosing regimen is the intended regimen for Part 2. However, if the aggregate PK and safety data indicate similar safety but higher cumulative exposure with the QW dose schedule, this schedule may also be evaluated in Part 2 in an additional cohort of 25 to 26 subjects, once the MTD or a tolerated dose below the MTD is identified in Part 1B. Treatment doses in the cohort expansion groups will not exceed the MTD.

Five expansion cohorts will be restricted to these tumor types 1) mesothelioma 2) pancreatic 3) ovarian 4) NSCLC, and 5) gastric cancer. Enrollment in cohort expansion will be determined by the mesothelin expression of the archived tumor sample (or fresh tumor sample if archived sample is not available).

The enrollment in each expansion cohort will be guided by a Simon 2-Stage design framework (see [Table 8.1-1](#)) exploring efficacy in the following 2 populations: [REDACTED]

Anti-tumor activity will be assessed initially in approximately 12 to 15 evaluable subjects per tumor type (Stage 1) treated in each monotherapy cohort, with the option to stop enrolling in a cohort without an initial anti-tumor activity signal. The number of subjects needed for the Stage 1 review is guided by a Simon 2-Stage design as shown in Table 8.1-1 below for each tumor type with futility boundaries as follows: after Stage 1, if none of the first 15 evaluable subjects in the gastric or pancreatic cohorts, if  $\leq 2$  of the first 12 with mesothelioma, or  $\leq 1$  of the first 14 with NSCLC or ovarian cohort demonstrate clinical activity, enrollment in the cohort meeting criteria may be stopped for this population.

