### 3.1.3.2 Part 3B (Dose Expansion)

The purpose of the cohort expansion will be to assess preliminary anti-tumor efficacy, expanded safety experience, and PD effects of BMS-986148 in combination with nivolumab. Additional subjects will be treated after the completion of Part 3A, at the MTD or at an alternate dose below the MTD as agreed upon by the BMS Medical Monitor and investigators. Five expansion cohorts will be restricted to these tumor types: 1) mesothelioma, 2) pancreatic, 3) ovarian, 4) NSCLC, and 5) gastric cancer. Enrollment in cohort expansion will be determined by the mesothelin expression of the archived tumor sample (or fresh tumor sample if archived sample is not available).

The enrollment in each combination expansion cohort will also be guided by a Simon 2-Stage design framework (see [Table 8.1-2](#)), exploring efficacy in the

Anti-tumor activity will be assessed initially in approximately 11 to 14 evaluable subjects per tumor type treated in a combination cohort, with the option to stop enrolling in a cohort without an initial anti-tumor activity signal. The number of subjects needed for the Stage 1 review is guided by a Simon 2-Stage design, assuming ORR as shown in [Table 8.1-2](#) for each tumor type with futility boundaries as follows: after Stage 1, if 0 or 1 of the first 11 evaluable subjects in the gastric or pancreatic cohorts, 0 or 1 of the first 14 in the evaluable ovarian cohorts,  $\leq 2$  of the first 12 with mesothelioma cohort, or  $\leq 1$  in the first 10 in the NSCLC cohort show clinical activity, enrollment in the cohort meeting criteria may be stopped.

Evaluation of efficacy will occur independently in each tumor cohort. At the time of the Stage 1 efficacy assessment, subjects will be enrolled to include sufficient numbers in both the populations to allow an initial (Stage 1) efficacy assessment. If there is a lack of signal for preliminary efficacy (number of responders not exceeding the boundary), and after evaluation of all available data, enrollment may be stopped in that population. Otherwise, additional subjects will be treated in Stage 2 for the population in which there was an initial signal.

As described for the monotherapy expansion, the above numbers are approximate, and enrollment may continue during the evaluation of the interim data.

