## **8 STATISTICAL CONSIDERATIONS**

### **8.1 Sample Size Determination**

Dose Escalation: In the monotherapy dose escalation part of the study, ie, both Parts 1A and 1B, a total of approximately 30 and 24 evaluable subjects are expected to be treated, respectively. The exact sample size per dose level cannot be precisely determined but depends on the observed DLT and will be guided by the mTPI design, with a target DLT rate of 27% (25% to 29%), based on Bayesian modeling and posterior inference. Between 2 and up to 13 DLT evaluable subjects may be enrolled to a given monotherapy cohort in Part 1A. Treating additional subjects beyond the 13 would be unlikely to alter the decision specified by the mTPI algorithm. In the combination dose escalation part (Part 3A), a total of approximately 12 evaluable subjects are expected to be treated across 2 dose levels, with the sample size per dose level guided by a mTPI design with target DLT rate of 29% (28% to 31%).

Cohort Expansion: During this part of the study, approximately up to 25 to 26 subjects in the population of interest [REDACTED] are expected to be treated in each tumor cohort at the MTD or alternate dose below the MTD (as determined from dose escalation), or other agreed dose level. This number per cohort is based on achieving a reasonable precision of the ORR and adequate control on the false negative rate (FNR) and false positive rate (FPR) (assuming a historic and target response rate as shown for monotherapy cohorts below):

In a cohort of 25 marker positive subjects, if 5 or 6 responses are observed (eg, for gastric or pancreatic cohorts), then the ORR 90% confidence intervals (CIs) are (8.2%, 37.5%) and (11%, 42%), respectively. If 7 responses are observed (eg, NSCLC and ovarian cohorts), then the 90% CI is (14%, 46.2%), and if 8 or 9 responses are observed (eg, mesothelioma cohort), then the 90% CIs for ORR are: (17%, 50.4%) and (20%, 54.4%), respectively. These calculations are based on the Clopper-Pearson method for exact CIs.

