In addition, 25 subjects per cohort provide the following FNR and FPR under assumptions of expected true ORR. If the true ORR is 40% (eg, mesothelioma), then with 25 subjects in a cohort there is 97% and 93% chance of observing at least 6 or 7 responses, respectively, and there is 7% chance of observing 6 or fewer responses (FNR). If the true ORR for this tumor is only 20% (rather than 40%), then there is 22% and 11% chance respectively of observing at least 7 and at least 8 responses among 25 subjects (FPR).

Similarly if the true ORR is 20% (eg, gastric and pancreatic cohorts), then there is 97% and 90% probability of observing at least 2 or 3 responses respectively, among 25 subjects and 10% of observing 2 or fewer responses (FNR). If the true ORR for these tumors is 10% (rather than 20%) then there is 24% and 10% chance, respectively, of observing at least 4 and at least 5 responses (FPR).

If the true ORR is 30% (eg, NSCLC and ovarian cohorts), then there is 91% and 81% probability of observing at least 5 or 6 responses, respectively, in 25 subjects and 9% of observing 5 or fewer responses (FNR). If the true ORR for these tumors is 15% (rather than 30%) then there is 16% and 7% chance, respectively, of observing at least 6 and at least 7 responses (FPR).

The Simon 2-Stage design will be used in the monotherapy and nivolumab combination expansion cohorts, with a minimum of subjects treated initially as per the Stage 1 n of [Table 8.1-1](#) and [Table 8.1-2](#) below. Efficacy will be explored in both the [REDACTED] populations; there will be no adjustment for multiple comparisons. In each of monotherapy or combination cohorts after a minimum number of subjects (n for Stage 1) are treated, there will be an initial evaluation of efficacy independently in each cohort. If there is a lack of signal in either population, then treatment in that cohort may be stopped in that population; if there is an initial efficacy signal, subjects will continue to be treated in Stage 2 for the population in which there was a signal. [REDACTED]

The above results will inform potential early decisions and guide planning/operations or early termination after taking into consideration additional data, for example, duration of response

and/or SD and safety. The operational characteristics of these Simon 2-Stage designs are provided in the following tables.

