**Table 8.1-1: Monotherapy Operating Characteristics for 2-Stage Simon Design**

Tumor Type	Historic ORR (%)	Target ORR (%)	Stage 1/ Total n	Stage 1 a Futility Boundary	Alpha / Power	Early Stopping Probability
Gastric	10	20	15 / 25	0	0.24 / 0.76	0.21
Mesothelioma	20	40	12 / 25	2	0.10 / 0.80	0.45
NSCLC Adeno	15	30	14 / 26	1	0.18 / 0.82	0.36
Ovarian	15	30	14 / 26	1	0.18 / 0.82	0.36
Pancreatic	10	20	15 / 25	0	0.24 / 0.76	0.21

a Number of responses indicating the cut-off for lack of efficacy signal.  
n: number of subjects; NSCLC: non-small cell lung carcinoma; ORR: objective response rate.

Similarly the operating characteristics of the 2-stage Design in the expansion cohort are shown in Table 8.1-2 below:

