## 5 SAMPLE SIZE AND POWER

Dose Escalation: In the dose escalation part of the study, i.e., both Part 1A and 1B, the sample size per dose level cannot be precisely determined but depends on the observed DLTs and the decision rules of mTPI. Between 2 and up to 13 DLT evaluable subjects may be enrolled to a given cohort. Treating additional subjects beyond the 13 would be unlikely to alter the decision specified by the mTPI algorithm.

Cohort Expansion: During this part of the study approximately 25 subjects with high expression of mesothelin are expected to be treated in each tumor cohort at the maximally administered dose or at a dose near the MTD (as determined from dose escalation). This number is based on achieving a reasonable precision of the objective response rate (ORR) and adequate control on the false negative rate (FNR) and false positive rate (FPR) (assuming a historic and target response rate). In a cohort of 25 marker positive subjects if 5 or 6 responses are observed (e.g. for gastric or pancreatic cohorts) then the ORR 90% CI are (8.2%, 37.5%) and (11%, 42%), respectively. If 7 responses are observed (e.g. NSCLC cohort), then the 90% CI is (14%, 46.2%), and if 8 or 9 responses are observed (e.g. mesothelioma or ovarian cohorts), then the 90% CI for ORR are: (17%, 50.4%) and (20%, 54.4%), respectively. These calculations are based on the Clopper- Pearson method for exact confidence intervals.

In addition, 25 subjects per cohort provide the following FNR and FPR under assumptions of expected true ORR. If the true objective response rate (ORR) is 40% (e.g. mesothelioma and ovarian cohorts), then with 25 subjects in a cohort there is 97% and 93% chance of observing at least 6 or 7 responses, respectively, and there is 7% chance of observing 6 or fewer responses (false negative rate). If the true ORR for these tumors is only 20% (rather than 40%), then there is 22% and 11% chance respectively of observing at least 7 and at least 8 responses among 25 subjects (false positive rate).

Similarly if the true ORR is 20% (e.g. gastric and pancreatic cohorts), then there is 97% and 90% probability of observing at least 2 or 3 responses respectively, among 25 subjects and 10% of observing 2 or fewer responses (false negative rate). If the true ORR for these tumors is 10% (rather than 20%) then there is 24% and 10% chance respectively, of observing at least 4 and at least 5 responses (FPR).

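### Protocol 8.1 misstates two operating characteristics: the NSCLC/ovarian false negative rate at 5 or fewer responses is 19%, not 9%, and mesothelioma early stopping is 0.56, not 0.45

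*Protocol*

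**What the plan says.** Protocol section 8.1 rests the number of subjects per expansion cohort on the precision of the ORR and on "adequate control on the false negative rate (FNR) and false positive rate (FPR"). It then says that "25 subjects per cohort provide the following FNR and FPR under assumptions of expected true ORR", and works through three tumor groups.

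For NSCLC and ovarian cancer, at a true ORR of 30%, it says "then there is 91% and 81% probability of observing at least 5 or 6 responses", and closes the sentence with "in 25 subjects and 9% of observing 5 or fewer responses (FNR"). The next sentence gives false positive rates at a true ORR of 15%: 16% for at least 6 responses and 7% for at least 7.

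Tables 8.1-1 (monotherapy) and 8.1-2 (nivolumab combination) give the Simon two-stage designs. The mesothelioma row is the same in both: "Mesothelioma 20 40 12 / 25 2 0.10 / 0.80 0.45". Read across, that is historic ORR 20%, target ORR 40%, 12 subjects in Stage 1 out of 25, futility boundary 2, alpha 0.10, power 0.80 and early stopping probability 0.45. Sections 3.1.2 and 3.1.3.2 repeat the Stage 1 rule as 2 or fewer "of the first 12 with mesothelioma" and 2 or fewer "of the first 12 with mesothelioma cohort".

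**The concern.** Two printed probabilities disagree with the designs they describe.

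In the NSCLC/ovarian sentence, at least 6 responses and 5 or fewer responses are complementary events. Their probabilities must sum to 100%, but as printed they sum to 81% + 9% = 90%. The 9% is one of three false negative rates offered in support of the cohort size, and it covers two of the five tumor types.

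The mesothelioma early stopping probability is too low for 12 subjects and a boundary of 2 at a 20% response rate. A reader would underestimate how often a cohort with only the historic response rate meets the Stage 1 futility criterion. The value 0.45 might also be the trace of a different Stage 1 size, in which case the rule itself would need reconciling before it is used.

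**Working it through.** **Inputs.** From Protocol 8.1: cohort size 25; true ORR 30% (target) and 15% (historic) for NSCLC/ovarian. From Tables 8.1-1 and 8.1-2: Stage 1 size, boundary and historic ORR for each row. A count at or below the boundary means no efficacy signal. All probabilities are exact binomial, P(X ≤ k) = Σ C(n,x) pˣ (1−p)ⁿ⁻ˣ for x = 0 to k.

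**1. NSCLC/ovarian, n = 25, p = 0.30**

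- The plan's own figures first: P(X ≥ 5) = 0.910 and P(X ≥ 6) = 0.807. The printed 91% and 81% reproduce.
- P(X ≤ 4) = 1 − 0.9095 = 0.0905.
- P(X = 5) = 53130 × 0.3⁵ × 0.7²⁰ = 0.1030.
- P(X ≤ 5) = 0.0905 + 0.1030 = 0.1935, or 19%.

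The printed 9% is therefore the probability of 4 or fewer, the complement of the 91%. Using n = 26 does not rescue it: P(X ≤ 5) = 0.163 and P(X ≤ 4) = 0.073.

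The other two false negative rates in the section reproduce at their stated cut-offs: 0.074 for mesothelioma (printed 7%) and 0.098 for gastric/pancreatic (printed 10%).

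False positive rates at p = 0.15: P(X ≥ 6) = 0.162 and P(X ≥ 7) = 0.070, matching the printed 16% and 7%. A false negative rate of 9% belongs to a cut-off of at least 5, where the false positive rate is P(X ≥ 5) = 0.318. No single cut-off with 25 subjects gives 9% and 16% together.

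As a side check, Table 8.1-1 prints power 0.82 for these cohorts. Exact enumeration of the 14/26 design with success at 6 or more gives 0.825, a miss rate of 17.5%. This is a two-stage value for 26 subjects, so it is not the same quantity, but it sits near 19% and not near 9%.

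**2. Early stopping probability, P(X ≤ boundary) at the historic ORR**

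| Row | Stage 1 n / boundary | Historic ORR | Printed | Recomputed |
|---|---|---|---|---|
| Gastric, pancreatic (monotherapy) | 15 / 0 | 10% | 0.21 | 0.206 |
| NSCLC (monotherapy), ovarian (both tables) | 14 / 1 | 15% | 0.36 | 0.357 |
| Gastric, pancreatic (combination) | 11 / 1 | 10% | 0.70 | 0.697 |
| NSCLC (combination) | 10 / 1 | 15% | 0.54 | 0.544 |
| Mesothelioma (both tables) | 12 / 2 | 20% | 0.45 | **0.558** |

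The four rows that reproduce settle what the column means. For mesothelioma:

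0.8¹² + 12 × 0.2 × 0.8¹¹ + 66 × 0.2² × 0.8¹⁰ = 0.0687 + 0.2062 + 0.2835 = 0.5583.

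Other readings of the printed design do not give 0.45: boundary 1 gives 0.275, an ORR of 40% gives 0.083, and the complement is 0.442. Values near 0.45 need a different design or rate: 14 subjects with boundary 2 (0.448), 19 with boundary 3 (0.455), or a true ORR near 23% (0.455).

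**3. Which Stage 1 size do alpha and power support?**

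The tables do not print the final cut-off. Taking success as 8 or more of 25, back-calculated from the printed alpha and power, and summing P(Stage 1 count = x) × P(at least 8 − x further responses) over x above 2:

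- n₁ = 12: alpha 0.099, power 0.815.
- n₁ = 14: alpha 0.106, power 0.838.

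The printed 0.10/0.80 is closer to 12.

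**4. Size for mesothelioma enrolment**

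If the boundary is followed, expected enrolment at ORR 20% is 12 + 13 × (1 − 0.5583) = 17.7, against 12 + 13 × (1 − 0.45) = 19.2 from the printed value.

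**The case against.** The strongest reply concerns weight. Nothing in the plan depends on either figure. No formal hypothesis is tested. The futility boundaries are non-binding: stopping is optional, follows a review of all available data, and the numbers are described as approximate. The confidence intervals that also support the cohort size are correct. A careful reader sees the true miss rate from the 81% and, roughly, from the 0.82 power. The mesothelioma enrolment gap is about 1.5 subjects, and stopping an inactive cohort more often than stated is no harm. All of this stands and limits the consequence. It does not make the figures right, and the section offers them as design justification.

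Two further points are fair:

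- The NSCLC/ovarian sentence could be repaired the other way, by keeping 9% and writing 4 or fewer. That would be arithmetically correct. However, the following sentence starts its false positive rates at 6 or more, and the power in Table 8.1-1 matches success at 6 or more, so 19% at 5 or fewer fits the section better.
- The alpha/power evidence for 12 mesothelioma subjects is supportive, not decisive. The final cut-off is inferred, the computed power of 0.815 is not exactly 0.80, and the column is not always an exact value. For example, the gastric combination design gives 0.078/0.841 with success at 5 or more, against a printed 0.10/0.84. If the column shows design limits, 12/25 meets them and 14/25 does not (alpha 0.106). Twelve is likelier, but the sponsor should confirm it.

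The gastric/pancreatic false negative and false positive rates in Protocol 8.1 and SAP section 5 are quoted at different cut-offs. Each is correct as labeled, so that is a matter of presentation and not an error.

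**Conclusion.** Both errors are confirmed.

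- At the cut-off the protocol states, the NSCLC/ovarian false negative rate is 19.3%, more than twice the printed 9%. This needs no assumption beyond the 25 subjects and the 30% ORR in the sentence itself.
- The mesothelioma early stopping probability is 0.56, not 0.45, in both tables. This takes the printed Stage 1 size, boundary and historic ORR as intended. It does not depend on the inferred final cut-off.

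On the printed design these are errors in reported figures, not in the rules. The remaining uncertainty is whether 0.45 was computed for 14 Stage 1 subjects. The tables and sections 3.1.2 and 3.1.3.2 agree on 12. The point should be fixed, but it does not undermine the design.

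**What to change.** 1. In Protocol 8.1, change the NSCLC/ovarian false negative rate for 5 or fewer responses from 9% to 19%.
2. Have the sponsor confirm the mesothelioma Stage 1 size. If it is 12, print 0.56 for early stopping in Tables 8.1-1 and 8.1-2. If 14 was intended, reconcile the Stage 1 size and the alpha/power in both tables with sections 3.1.2 and 3.1.3.2.
3. Optional: note in 8.1 that the false negative and false positive rates are single-stage values for 25 subjects and differ slightly from the two-stage tables. The gastric/pancreatic pair could also be quoted at one cut-off, in 8.1 and SAP section 5; at least 4 of 25 gives 23% and 24%, in line with 0.24/0.76 in Table 8.1-1.

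The cost is one phrase and one cell in each of two tables. With 12 confirmed, no sample size, boundary or decision rule changes. SAP section 5 contains neither the 30% sentence nor the Simon tables, so items 1 and 2 need no SAP edit.

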**Table 8.1-1: Monotherapy Operating Characteristics for 2-Stage Simon Design**

Tumor Type	Historic ORR (%)	Target ORR (%)	Stage 1/ Total n	Stage 1 a Futility Boundary	Alpha / Power	Early Stopping Probability
Gastric	10	20	15 / 25	0	0.24 / 0.76	0.21
Mesothelioma	20	40	12 / 25	2	0.10 / 0.80	0.45
NSCLC Adeno	15	30	14 / 26	1	0.18 / 0.82	0.36
Ovarian	15	30	14 / 26	1	0.18 / 0.82	0.36
Pancreatic	10	20	15 / 25	0	0.24 / 0.76	0.21

a Number of responses indicating the cut-off for lack of efficacy signal.  
n: number of subjects; NSCLC: non-small cell lung carcinoma; ORR: objective response rate.

Similarly the operating characteristics of the 2-stage Design in the expansion cohort are shown in Table 8.1-2 below:

**Table 8.1-2: Nivolumab Combination Operating Characteristics for 2-Stage Simon Design**

Tumor Type	Historic ORR (%)	Target ORR (%)	Stage 1/ Total n	Stage 1 a Futility Boundary	Alpha / Power	Early Stopping Probability
Gastric	10	30	11 / 25	1	0.10 / 0.84	0.70
Mesothelioma	20	40	12 / 25	2	0.10 / 0.80	0.45
NSCLC Adeno	15	40	10 / 22	1	0.10 / 0.90	0.54
Ovarian	15	30	14 / 26	1	0.18 / 0.82	0.36
Pancreatic	10	30	11 / 25	1	0.10 / 0.84	0.70

a Number of responses indicating the cut-off for lack of efficacy signal.  
n: number of subjects; NSCLC: non-small cell lung carcinoma; ORR: objective response rate.

## 8.2 Populations for Analyses

- All Enrolled Subjects: All subjects who sign an informed consent form.
- All Treated Subjects: All subjects who receive at least 1 dose of study medication.
- PK Subjects: All subjects who receive at least 1 dose of BMS-986148 and have available serum and plasma concentration data.

- Immunogenicity (ADA) Population: all treated subjects who had baseline and at least 1 post-treatment immunogenicity assessment
- ECG Evaluable Population: all treated subjects who had a baseline ECG and at least 1 on-study ECG.
- Response Evaluable Population: all treated subjects who had baseline tumor measurement and at least 1 other tumor measurement after treatment, clinical progression, or death prior to the first on-treatment tumor assessment.

### **8.3 Endpoints**

#### **8.3.1 Primary Endpoint(s)**

Incidence of AEs at worst grade, SAEs at worst grade, AEs leading to discontinuations, deaths, and frequency of laboratory test toxicity grade shifting from baseline. Safety will be evaluated from the time that the subject signs the informed consent, and for up to 60 days (or 100 days for combination therapy) after the last dose of study drug.

#### **8.3.2 Secondary Endpoint(s)**

##### **8.3.2.1 Pharmacokinetics**

The PK of total antibody, active ADC, unconjugated tubulysin, and nivolumab will be characterized using the following endpoints (previously defined in [Section 5.5](#)):

- Cmax
- Tmax
- Ctau
- Ctrough
- AUC(0-t)
- AUC(TAU)
- T-HALF
- CLT
- Vss
- Vz
- AI\_AUC
- AI\_Cmax
- AI\_Ctau
- Cavg

### **8.3.2.2 Efficacy**

Efficacy based on RECIST version 1.1 or Modified RECIST for malignant pleural mesothelioma (Appendix 4) will be assessed using the following secondary endpoints:

- Best overall response (BOR): defined as the best response designation over the study as a whole, recorded between the dates of first dose until the last tumor assessment prior to subsequent therapy. CR or PR determinations included in the BOR assessment must be confirmed by a second scan performed no less than 4 weeks after the criteria for response are first met. For those subjects who have surgical resection, only pre-surgical tumor assessments will be considered in the determination of BOR.
- ORR: defined as the total number of subjects whose BOR is either a CR or PR divided by the total number of subjects in the population of interest.
- Duration of response: defined as the time between the date of first response and the subsequent date of objectively documented disease progression or death, whichever occurs first. For those subjects who remain alive and have not progressed or received subsequent therapy, duration of response will be censored on the date of last tumor assessment
- PFS: defined as the time from the first dose of study medication to the date of the first objective documentation of tumor progression or death due to any cause. Subjects who did not progress nor died will be censored on the date of their last tumor assessment. Subjects who did not have any on-study tumor assessments will be censored on the date of the first dose of study medication.
- PFS rate at week 't': defined as the proportion of subjects who remain progression free and surviving at 't' weeks (eg, t=12, 24, and 36 weeks, and following the corresponding planned tumor scan visit). The proportion will be calculated by the product-limit method (Kaplan-Meier estimate) which takes into account censored data.

[figure not shown]
